8.3 Randomisation

On receipt of the Informed Consent Form, the LCTU utilises the UKLS database management system to randomise individuals. The UKLS database will automatically check eligibility and if eligibility is confirmed will randomise the participant to either the CT screening arm of the trial or the control arm on a 1:1 ratio, using a computer generated random number algorithm. Participants will be notified of their randomised allocation by the LCTU. If the participant has been randomised to the CT arm of the trial the notification letter will include an invitation to have the CT scan and an appointment for the CT scan.

9 Lung cancer Screening

9.1 Introduction

Participants will be randomised to either receive intervention CT scan (Arm A) or to a control arm (Arm B) no intervention.

9.2 Arm A

Participants randomised to Arm A will receive a low dose CT scan.

9.3 Arm B

Participants randomised to Arm B will have no intervention.

9.4 Radiological Protocol for the UK Lung Cancer Screening Trial

9.4.1 CT Equipment Requirements

All participating sites will use 16 or higher (e.g. 64) channel multi-detector CT (MDCT), whether fixed site or mobile, calibrated according to the manufacturer's specifications. For consistency, the same fixed site CT machine should ideally be used throughout the course of the study.

The rationale for using a 16 or higher channel MDCT platform is that the majority of screen detected nodules will be small (3-10 mm) and require optimal spatial resolution for accurate and reproducible evaluation including nodule volume measurement. Only MDCT enables data acquisition within a single breath-hold at the narrow detector collimations and slice thicknesses required multi-detector CT. Although 64 slice CT is considered relatively advanced, by study completion such technology is likely to be the norm. The use of 16 slice or higher MDCT platforms will ensure that the screening CT, the test under consideration, is of the highest quality and the primary endpoint is not compromised by inferior image quality.

During the 14 month period of the Pilot Study during which CTs are acquired, the two sites will use a mobile CT (private sector) for a six week period; the mobile machine will be of the same basic technical specification (i.e. at least 16 channel MDCT).

9.4.2 CT Image Acquisition Protocol (applicable to fixed site and mobile CT)

Preparation

Participants' weight and height will be ascertained prior to scanning to permit selection of exposure factors.

Subject Position: Participants should lie supine on the CT table with arms above their head and thorax in the midline of the scanner. Subject comfort should be optimised and maximal inspiration rehearsed prior to the scan to minimise motion during the CT. Imaging should be performed during suspended maximal inspiration. No intravenous contrast material will be administered.

Localiser: Sites should use their standard scanogram to localise the start and end positions of the scan. The frontal localiser should be performed in the PA projection

(tube at gantry bottom, patient supine) and at the lowest possible setting (e.g., 80 kVp, 20 mAs) to minimise breast dose.

Volumetric CT scan: The lung parenchyma (lung apices to bases) must be scanned in its entirety in a single craniocaudal acquisition. The field of view (FOV) selected as the smallest diameter as measured from widest point of outer rib to outer rib large enough to accommodate the entire lung parenchyma (usually no more than 35cm). Thin detector collimation (0.5 – 0.625mm) will be used with a pitch of 0.9-1.1. Scan time should usually be in the region of 5 seconds but must not exceed 10 seconds to avoid respiratory motion artefact. Sufficient delay time must be given after completion of the inspiratory command to ensure inspiration is complete prior to scan commencement. A start delay of 5-7s is usually appropriate, during which breathing commands are given.

Exposure factors: Radiation exposures will be as low as possible whilst maintaining good image quality. The CT dose index (CTDIvol) will be kept below 4 mGy, with the effective radiation dose well below 2 mSv. The kVp and mAs settings will be varied according to participant body habitus:

	Slim subjects (<50 kg BW)	Standard (50-90 kg BW)	Large (>90 kg BW)
kVp setting	100 kVp	120 kVp	140 kVp
mAs settings*	*depending on scanner type adjusted to achieve CTDI given below		
CTDIvol	0.8 mGy	1.6 mGy	3.2 mGy
Effective dose	<0.5 mSv	<0.8 mSv	<1.4 mSv
Effective dose including scout view (0.2mSv)	<0.7 mSv	<1.0mSv	<1.6mSv

If available, adaptive filtering should be used to optimise image quality, especially in the shoulder region and lung apices. Dose modulation packages should be used according to local practice.

Image reconstruction: should rely on thin collimation and overlapping 1mm-volumetric data. Image reconstruction should be standardised and used for any subsequent follow-up examinations.

The reconstruction parameters will be:

Reconstruction Algorithm	Reconstruction Slice thickness	Reconstruction Increment	Reconstruction FOV
Moderate spatial frequency / soft tissue (eg. GE Standard, Philips B, Siemens B30f).	1mm	0.7mm	Entire lung parenchyma

9.4.3 Image Interpretation

Image interpretation is performed on 3D CT workstations which permit scrolling through the data set with variable thickness and orientation using multi-planar reformations (MPR), Maximum Intensity Projection (MIP) and Minimum Intensity

Projections (MinIP). Nodule detection is simplified by using MIP of around 10mm thickness. Additional reconstructions of image data may be necessary for clarification. Axial and coronal or sagittal planes should also be reviewed. All three planes are helpful for assigning a nodule to a lung segment (for identification and follow-up). Nodule characterisation is usually based on thin MPR. MinIP may be helpful for evaluating the bronchial tree.

All scan data acquired from trial participants will be archived and retained at the local site. The data will be sent in standardised DICOM 3.0 format in a point-to-point fashion using the secure NHS N3net to a firewall protected server at the central site for second reading and secondary archiving.

9.4.4 Methodology for CT Reading

Establishing and maintaining accurate CT interpretation is crucial for the success of the trial. To this end, all baseline CT studies will be interpreted both locally and centrally (double reading) to optimise the sensitivity and specificity of CT screening.

The pilot study will aim to optimise the method of reporting including the investigation of the effectiveness of different methods of training observers and the appropriateness of radiologists versus non-radiologists as local site readers. This will be undertaken in both the pre-trial training sessions and by continuous assessment in the two centre pilot study.

9.4.5 Local and Central Reading Personnel

Local Site Reading, Reader 1

The pilot trial will investigate the practicality and effectiveness of the use of radiographers as readers. The primary purpose of this reader, once appropriately trained, will be to identify and measure pulmonary nodules using volumetric analysis software (Siemens LungCare), and record them on the UKLS web-based database. A benefit of developing this expertise will be to the local department which will already be faced with the increasingly frequent challenge of dealing with incidentally detected pulmonary nodules on CT.

For the specific tasks of CT nodule detection and categorising nodules into one of the four grades in the Care Pathways, radiological expertise is not required. The requirement to work in an uninterrupted and focused fashion is more important than medical/radiological expertise. Systematic CT reading is time-consuming; subsequently entering information into the UKLS database takes more time. It is likely that a technician or radiographer is a more appropriate reader than a highly trained (and relatively expensive) radiologist who, in a clinical setting, is unlikely to be able to undertake such reading and data entry without interruption.

Local Site Reading, Reader 2 – Consultant

The purpose of the second reader is to act as trainer and mentor to Reader 1 and confirm or refute findings about which Reader 1 is uncertain. As part of the pilot study there will be the opportunity for readers 1 and 2 to read independently, allowing a comparative study of observer performance to be undertaken. Furthermore, the two pilot centres could also read each other's cases to increase the

power of this comparison (projected numbers approx 100 cases/month for 14 months in each of two centres).

Options for local reporting protocol (Pilot) methodology include:

1. Reader 1 then Reader 2 – The technologist (Reader 1) serves as a first reader (flags nodules, enters all data into database), then the radiologist (Reader 2) works as a second independent reader (flags nodules); Reader 1 enters (agreed) nodule data into the database.
2. Reader 2 then Reader 1 – Reader 2 marks any nodule that he/she wants to be entered and the Reader 1 takes care of database entries (time saving).
3. Independent/blinded – followed by consensus or arbitration. Reader 2, the radiologist, serves as a first reader (marks nodules and saves XML file with nodule data), Reader 1, the technologist, serves as a second independent reader (marks nodules) and then takes care of transferring all data into the database.

The third option would have the advantage of allowing Reader 1 to learn “on the fly” and the continuous feedback would show at what point Reader 1 reaches or supersedes Reader 2’s detection of nodules.

By the end of the Pilot study there will be a formal review, based on the outcome of the Readers’ performance, as to the optimal method of CT reading for the Main trial. It is likely that the Reader 2 (radiologist) will not be required routinely.

The CT readings will have one of three possible outcomes:

Benign/insignificant nodule or no nodules – no further action

Nodules requiring follow up

Nodule requiring other intervention e.g. MDT opinion and staging CT

Central Site Reading, Reader 3

All baseline CTs will be read by a central reader, Reader 3 (consultant radiologist), who will be unaware of the conclusion of the local centre’s reader. The central site reading will take place within two weeks of the first, local site, reading. For quality control purposes 10% of follow up CT scans will be read by a central reader. In addition, the central reader will be available to deal with ad-hoc queries on particular cases from the Radiologists at the trial sites.

Arbitration Reading, Reader 4

Occasionally, there will be significant discordances regarding the presence or absence of a nodule, interval growth or significant extra pulmonary finding and these will require review and arbitration by a fourth reader, Reader 4. Such readers will be one of a designated panel of experts, drawn from the UKLS Radiology Group.

The local site reader will receive the central reading report, with discrepancies, if any, highlighted. In case of discordance, the local site reader may find it necessary to change the initial report; in this event, the updated record is submitted to the central site. The site reader sends the final report to the trial participant’s general practitioner.

9.4.6 Lung Nodule Characterisation

For each nodule evaluated, various characteristics (listed below) will be entered by the reader in a customised electronic data collection form, integrated with Siemens LungCare software and the calculated sizes and volumes generated by the software will be automatically uploaded into the UKLS Management System (on licence from NELSON investigators) immediately after completion of the reading.

Nodule definitions:

A nodule is characterised as a small approximately spherical, non-linear circumscribed focus of abnormal soft tissue.

A non-calcified nodule is classified as non-calcified in the absence of a benign pattern of calcification.

For all nodules the following characteristics will be recorded on the UKLS database: Maximum dimensions in x, y and z direction, minimum, maximum and mean diameter, size, volume, density, location (central versus peripheral, lung segment, section number and table position), and their surface characteristics.

Nodules will be categorised by:

NUMBER

The characteristics of each nodule will be recorded separately. The number of nodule evaluations per CT examination is unlimited, but if there are more than 20 nodules less than 8 mm in size, the individual characteristics of the nodules will not be recorded separately.

SIZE

Nodules will be categorised as:

(n.b. nodules $\leq 3\text{mm}$ are for the purposes of the trial ignored and not recorded)

Solid nodules

Category 2 (Small). If intraparenchymal with a volume of 15-49 mm³. If pleural or juxtapleural with a maximal diameter of 3.1 - 4.9 mm.

Category 3 (Medium). If intraparenchymal with a volume of 50-500 mm³. If pleural or juxtapleural with a maximal diameter 5 - 9.9 mm.

Category 4 (Large). If intraparenchymal with a volume $>500\text{ mm}^3$. If pleural or juxtapleural with a maximal diameter of 10 mm or greater.

Part solid and non-solid nodules (ground glass opacities)

Category 2 (Small). If the maximal non-solid component diameter is less than 5 mm and, in case of a solid component, if this component has a volume $<15\text{ mm}^3$.

Category 3 (Medium). If the non-solid component has a maximal diameter of more than 5 mm or, in case of a solid component, if the component volume is 15-500 mm³.

Category 4 (Large). If the solid component has a volume $>500\text{ mm}^3$.

POSITION

Nodules will be classified as central or peripheral. They will be defined as peripheral if the distance to the thoracic wall is less than one third of the total distance to the hilum. All nodules will be further categorised as:

- i. Intraparenchymal. No contact with the pleura, or fissures
- ii. Pleural based. Nodules with contact with the pleura
- iii. Juxtapleural. Nodules that are within 2 mm of the pleura

MORPHOLOGY

Nodules will be categorised as benign – Category 1 or not benign – Categories 2 to 4.

Category 1 Nodules will be classified as

Benign if they contain fat, or contain a characteristic benign pattern of calcification.

Sub-pleural lymph nodes will be recorded as such if they fulfil the following criteria: they lie within 5 mm of the pleura (or are within interlobar fissures) are < 8mm in diameter, are smooth bordered and ovoid and at least one interlobular septum radiating from surface is identified.

Category 2 to 4 nodules will be characterised by the following definitions and descriptions. These should be recorded for each nodule.

Solid – a nodule of homogeneous soft tissue attenuation. Solid nodules may have different outlines and these will be classified as smooth, polylobulated, spiculated or irregular. Smooth is defined as a continuous regular outline. Lobulation is defined as areas of bulging of the lesion contour. Spiculation is defined as the presence of strands extending from the lung margin into the lung parenchyma. Irregular is defined as not smooth, polylobulated, or spiculated.

Part-solid – a nodule of both ground-glass and soft-tissue attenuation

Non-solid/Ground glass opacity – a nodule composed of a focal area of hazy increased lung opacity

GROWTH CHARACTERISTICS

Volume doubling time category: < 400 days, 400-600 days, >600 days.

9.4.7 Summary of Categories of Nodules detected during Screening

Category 1 Benign nodules: Nodules fulfilling one of the following criteria; a benign pattern of calcification, fat, measuring less than 3 mm in diameter or volume <15 mm³. Sub-pleural lymph nodes fulfilling the following criteria: they lie within 5 mm of the pleura of the middle and lower lobes, are <8 mm in diameter, are smooth bordered and ovoid and have at least one interlobular septum radiating from surface.

Category 2 If solid and intraparenchymal with a maximal diameter of 3.1 - 4.9 mm or a volume of 15 - 49 mm³. If solid and pleural or juxtapleural with a max diameter of 3.1 - 4.9 mm. If non-solid or part solid with a max diameter of 3.1 - 4.9 mm. The solid component has a diameter of <3 mm and/or volume of <15 mm³. All non-solid/ground glass opacities independent of diameter (all to be recorded).

Category 3 If solid and intraparenchymal with a volume of 50 - 500 mm³. If solid and pleural or juxtapleural with a diameter 5 - 9.9 mm. If non-solid or part-solid with a diameter of the ground-glass component of >5mm. If part solid and the solid component has a volume of 15 - 500 mm³ or has a max diameter of 3.0 – 9.9 mm.

Category 4 If solid and intraparenchymal with a volume >500 mm³. If solid and pleural or juxtapleural with a diameter of ≥10 mm. If part solid and the solid component has a diameter of ≥10 mm or has a volume >500 mm³.

Management of newly identified nodules at Follow Up CT

If a new nodule is identified at 3 months the following will apply:

- 1) Readers will check that the nodule is genuinely new. If the nodule is identified on the baseline scan in retrospect, the volume doubling time will be calculated as if it had been identified and the appropriate algorithm followed as per the original UKLS protocol.
- 2) If the consensus reading is that the nodule is genuinely new and classified as category 1 or 2, then there will be no change to the existing algorithm and the participant will undergo a scan in 9 months (i.e. 12 months from baseline) (See “9 month” letter).
- 3) If the consensus reading is that the nodule is genuinely new and classified as larger than a category 2, then the participant will be recommended to have a follow up CT in 3 months. The reasoning behind this is because new nodules that have developed rapidly in this timeframe are likely to be inflammatory and have resolved within 3 months. (See new “incidence 3 month letter”)
- 4) At 3 months, if the nodule has resolved or is stable (VDT>400 days) the participant will continue as per the protocol and have their originally planned CT at 12 months from baseline (See new “6 months” letter)
- 5) At 3 months, if the nodule has grown significantly (VDT<400 days), the participant will be referred to the MDT.

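### Sections 9.4.6 and 9.4.7 define overlapping nodule categories, so one nodule can carry two categories and, if new at the 3-month scan, two follow-up schedules

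*Protocol*

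**What the plan says.** Section 9.4.6 gives the definitions and 9.4.7 is headed as their summary. They can be compared on three kinds of nodule.

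- **Ground-glass (non-solid) nodules.** In 9.4.6, Category 2 applies "If the maximal non-solid component diameter is less than 5 mm" and Category 3 "If the non-solid component has a maximal diameter of more than 5 mm". In 9.4.7, Category 2 first gives non-solid nodules a range of 3.1 to 4.9 mm, then adds "All non-solid/ground glass opacities independent of diameter (all to be recorded". Category 3 in the same section applies "If non-solid or part-solid with a diameter of the ground-glass component of >5mm".
- **Solid intraparenchymal nodules.** Section 9.4.6 uses volume alone: 15-49 mm³ for Category 2 and 50-500 mm³ for Category 3. Section 9.4.7 keeps the same volume band for Category 3 but defines Category 2 as "If solid and intraparenchymal with a maximal diameter of 3.1 - 4.9 mm or a volume of 15 - 49 mm³".
- **Benign sub-pleural lymph nodes (Category 1).** Section 9.4.6 accepts them where "they lie within 5 mm of the pleura (or are within interlobar fissures"), with no mention of lobe. Section 9.4.7 accepts them where "they lie within 5 mm of the pleura of the middle and lower lobes" and does not mention fissures. The other criteria (under 8 mm, smooth, ovoid, a radiating septum) are the same.

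Section 9.4.7 then ties category to action for a nodule judged genuinely new at the 3-month scan. Category 1 or 2 means a scan in 9 months; anything larger means a follow-up CT in 3 months.

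**The concern.** A classification that drives follow-up must give one answer per nodule. Here the ground-glass conflict lies inside 9.4.7 itself, so choosing one section over the other does not settle it. All three conflicts straddle the line between Category 2 and Category 3, or between benign and Category 3. That is the line on which the new-nodule schedule turns.

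The planned reading model makes this more pressing. Section 9.4.5 says that sorting nodules into the four grades does not need radiological expertise, and it expects that the local radiologist will probably not be needed routinely in the main trial. Such a model relies on the written rules. The pilot is also meant to choose the reading method from reader performance (9.4.5), graded on a discrepancy scale that depends partly on change of outcome (9.4.10). Two readers who each follow the protocol could be scored as disagreeing, and a fault in the definitions would be counted as reader error.

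**Working it through.** The check applies both sections' rules to the same hypothetical nodules. Diameters are converted with the sphere formula V = πd³/6. The spherical shape is an assumption; 9.4.6 describes nodules as roughly spherical.

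**Solid intraparenchymal band.**

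- Diameter at the lower limit of Category 3: d = (6 × 50/π)^(1/3) = 4.57 mm.
- Volume at the upper diameter limit of Category 2: V = π × 4.9³/6 = 61.6 mm³.
- A sphere of 4.57 to 4.9 mm (50 to 61.6 mm³) therefore meets the Category 2 diameter rule and the Category 3 volume rule of 9.4.7. Section 9.4.6 gives Category 3 only.
- Shape matters. An ellipsoid of 4.9 × 4.3 × 4.3 mm has V = π/6 × 4.9 × 4.3 × 4.3 = 47.4 mm³ and is Category 2 in both sections.

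**Side by side.**

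| Nodule | 9.4.6 | 9.4.7 |
|---|---|---|
| Pure ground-glass, 8 mm | 3 | 2 and 3 |
| Pure ground-glass, exactly 5.0 mm | none | 2 |
| Solid intraparenchymal sphere, 4.5 mm (47.7 mm³) | 2 | 2 |
| Solid intraparenchymal sphere, 4.7 mm (54.4 mm³) | 3 | 2 and 3 |
| Solid intraparenchymal ellipsoid, 4.9 × 4.3 × 4.3 mm (47.4 mm³) | 2 | 2 |
| Solid pleural or juxtapleural upper-lobe node, 6 mm, all other lymph-node criteria met | 1 | 3 |

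The last row follows because the node fails the lobe condition of 9.4.7 and then falls in its 5-9.9 mm band for pleural and juxtapleural nodules.

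**Same fault at two other edges of 9.4.7.** These concern the solid component of a part-solid nodule, again taken as a sphere. From 3.0 mm (14.1 mm³) to 3.06 mm (15 mm³) it is Category 2 by volume and Category 3 by diameter. From 9.85 to 9.9 mm (500 to 508 mm³) it is Category 3 by diameter and Category 4 by volume. These are slivers, but the same reconciliation should cover them.

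**Consequence.** For a genuinely new nodule at 3 months, the two schedules differ by 9 − 3 = 6 months to the next scan. The 8 mm ground-glass nodule, the 4.7 mm solid sphere and the 6 mm upper-lobe node can each be placed on either side.

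**The case against.** The best defence concerns the ground-glass sentence. Its closing words are an instruction to record, and 9.4.6 says that nodules of 3 mm or less are not recorded. The sentence could be an exception to that rule, with category still decided by the 5 mm limit on which both Category 3 definitions agree. This may be what was meant. It is not what is written: the sentence stands within the Category 2 definition and sets size aside, directly after that definition has given a size range.

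Other points stand in part:

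- The solid-nodule conflict is narrow and depends on shape. A reader might infer that every solid intraparenchymal nodule of 4.6 to 4.9 mm is affected; the ellipsoid above shows that this is false. Volume is also generated by software and uploaded automatically, which favours the volume rule in practice.
- The lymph-node conflict is clearest for upper-lobe nodes. Section 9.4.6 merely sets no lobe limit, and a fissural node may still lie within 5 mm of middle- or lower-lobe pleura and so qualify under 9.4.7.
- Safeguards exist. Readers must reach 80% concordance with a single NELSON standard (9.4.8), all baseline scans are read centrally (9.4.5), and the new-nodule rule is applied to a consensus reading. These may reduce divergence between readers, but a consensus applying 9.4.7 to an 8 mm ground-glass nodule still finds two categories.

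**Conclusion.** The point holds. The category definitions in 9.4.6 and 9.4.7 contradict each other, and 9.4.7 contradicts itself. The ground-glass conflict is the most serious, since it covers every pure ground-glass opacity above 5 mm. The solid-nodule conflict covers near-spherical nodules in a band of about 0.3 mm, and the lymph-node conflict covers mainly upper-lobe nodes. The consequence shown in the text is that a genuinely new nodule at the 3-month scan can be given either of two schedules. Reader-agreement results, and any screening-performance result that uses category, may also be affected.

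A reader might infer more than the document supports:

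- **Baseline recall.** Section 9.4.5 links the four grades to the care pathways, but the pathway figures are not shown. An effect on baseline recall is an inference.
- **The 30% work-up figure in 15.4.** Nothing says that Category 2 versus 3 feeds it. Section 4.4.1 treats repeat CT as a filter before clinical work-up, and 15.4 says that the figure is not a criterion for proceeding.
- **False-positive rate and specificity.** Section 15.5 plans these, but the protocol does not define a positive screen by category.
- **Numbers affected.** No nodule frequencies are given, so none can be computed.
- **Mortality.** The lung cancer mortality comparison is not directly altered.

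**What to change.** The investigators should reconcile 9.4.6 and 9.4.7 into one set of mutually exclusive and complete definitions. The same text should stand in both sections, in the database rules and in the reader training material. Which limits are right is a clinical decision for them; none is proposed here.

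For pilot data:

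- Recode nodules under the single definition, for descriptive and reader-agreement reporting, where diameter, volume, density and location are stored.
- Re-review archived scans for lymph-node cases that the stored fields cannot settle.
- Report recall as actually carried out separately. Recoding cannot change scans already scheduled, and a recall rate built on recoded categories would describe management that participants did not receive.

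The cost is a protocol amendment, a check of the database rules and a limited re-review of images. Recoding will be incomplete: where a scan shows more than 20 nodules under 8 mm, 9.4.6 does not have their individual characteristics recorded, so those cases cannot be recoded from stored data.
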